#### 8.10 Long term follow-up assessments

Randomised participants who have completed the treatment phase of the trial (visits 2-8) will be required to attend a 3-month follow-up visit (visit 9, 90 to 97 days after visit 2), and a 6-month follow-up visit (visit 10, 180-187 days after visit 2); there will also be an optional 12-month follow-up online assessment (see section 8.10.1). Table 2 (page 46) outlines which assessments will be carried out at visits 9 and 10.

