#### 8.12 Withdrawal criteria

Participants who withdraw before Visit 2 (Baseline) will be replaced by assigning successive screening IDs to eligible participants, but after completing eligibility checks and breathalyser on visit 2, participants will be randomised and will not be replaced.

Participants have the right to withdraw at any time and there is no obligation to provide reasons for withdrawal. Participants who discontinue any aspect of the trial treatment, would still be invited to complete the follow-up visits at 3 months (visit 9) and 6 months (visit 10), unless they fully withdraw from the trial. A participant cannot choose to discontinue one element of the treatment package, i.e. if they discontinue from IMP treatment they cannot continue with therapy/education or vice versa. Participants wishing to withdraw their consent from the trial should contact a member of their site trial team to make

their wishes known. In addition, the CI and/or PI may discontinue a participant from the trial at any time it is considered necessary for any reason including:

- Ineligibility (either arising during the trial or retrospectively)
- Significant non-compliance with treatment or trial requirements e.g. If the participant misses 2 consecutive infusions, as detailed in section 9.11
- An adverse event which requires discontinuation of the trial medication or results in inability to continue to comply with trial procedures
- Disease progression which requires discontinuation of the trial medication or results in inability to comply with trial procedures
- Consent withdrawn, loss of capacity or detention under Mental Health Act
- Pregnancy, see section 10.6.
- In the case of an overdose with ketamine, the participant will be withdrawn from the trial (see section 10.7)
- Positive urine screen for ketamine after randomisation. Participants would be withdrawn from treatment but invited to continue to 3-month and 6-month follow-up.

However, all efforts will be made to maintain participants in the trial where possible and to continue assessments as intended. If treatment is stopped for longer than 7 days in this trial, then it will not be possible to resume treatment. The reason for participant withdrawal will be recorded in the withdrawal/change in participation eCRF and medical notes (or source data file if no medical notes are available) within 24 hours of the site trial team becoming aware.

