# 9.12 Assessment of compliance with treatment

Compliance includes adherence to both to IMP and protocol trial procedures. The trial medication will be administered by the research medic/nurse only in the context of the participant attending the trial site facility. Participants will not be responsible for any trial medication. A member of the site team will ensure that the arrangements for each treatment visit are agreed with the participant. Where necessary, the site team will assist in transportation. If a participant fails to attend a clinic visit for the infusion then the site team will endeavour to contact the participant to identify the reason. Where possible an alternative appointment will be made within the infusion visit window (see Table 2 page 46). If the participant fails to attend a clinic visit for the follow-up day the site team will endeavour to contact the participant to identify the reason and where possible arrange an alternative visit within the follow-up visit window (see Table 2 page 46). All episodes of failure to attend visits will be recorded in the medical notes, eCRF and protocol deviation log (eCRF). If the participant misses 2 consecutive infusions, then they will be withdrawn from treatment and will be invited to attend follow up visits 9 and 10 as part of our intention to treat protocol. Non-compliance to the protocol trial procedures will be documented by the site team and reported to ExeCTU via the eCRF. Persistent non-compliance (attendance <80% for treatment visits i.e. visits 2-8) may lead the participant to be withdrawn from the trial.

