#### 10.7 IMP Overdose

We do not envisage an overdose as infusions are prepared by pharmacy or unblinded research nurses, and then administered by a research nurse/medic within the research site. Accidental administration of 50 times the higher protocol dose constitutes an overdose. In the event of an overdose, the participant should be observed closely for signs of toxicity. Appropriate supportive treatments should be provided if clinically indicated. ExeCTU and the Sponsor should be notified within 24 hours *via* the breach reporting eCRF. Local Trust procedures on incident reporting will also be followed. Overdoses will be observed from drug charts, or an anaesthetic response in the participant. If an SAE is associated with the overdose then this will be fully described in the SAE eCRF. In the case of a ketamine overdose, the participant will be withdrawn from treatment and will be invited to attend follow up visits 9 and 10 as part of our intention to treat protocol.

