# 11.3.1 Analysis sets

The primary statistical analysis will include observed data only.

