# 11.3.3 Handling of intercurrent events of primary estimands

Intercurrent events related to adherence to treatment (i.e. discontinuation/withdrawal) will be handled using the treatment policy strategy; the treatment effect is sought irrespective of the occurrence of an intercurrent event. This policy is in alignment with an ITT analysis. Deaths during the trial will be handled using the 'while alive' approach; participant data collected prior to death will be included in the analyses.

A principal stratum approach will be used to target the treatment effect in adherent participants (assuming that adherence status would be identical for a participant irrespective of the treatment group to which they were allocated). A per protocol analysis will compare adherent participants

REDACTED Version 8.0, 18/JUN/2024; IRAS ID: 1008179 MORE-KARE protocol Page 82 of 105

Participants will be considered as adherent if they received all three infusions at their allocated dose plus all their scheduled sessions as allocated. The per protocol approach is in alignment with a principal stratum approach. The resulting estimand therefore applies to the population of people who would be adherent to treatment as offered.

A per protocol analysis will be performed for the primary outcome and all secondary outcomes at 6month follow-up. There are limited opportunities within the trial for treatment switching

is no possibility for the participants to receive ketamine outside the trial, and participants are requested to refrain from beginning new psychological therapy during the active treatment phase. A participant could only receive the incorrect dose of ketamine if an error occurred in making up or administering the IMP.

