# 12 DATA MANAGEMENT

# 12.1 Data collection tools and source document identification

The primary data source will be trial-specific paper and electronic case report forms ((e)CRFs) and laboratory reports. Participants will complete trial questionnaires and this data will be transcribed into the secure, online trial database by blinded trial personnel. The questionnaires will be source data. Research nurses/medics will also collect various physical measurements on each trial participant, which will be documented in the medical notes and then transcribed into the trial database. Participants will be identified by a trial number allocated at the point of consenting which will ensure anonymity of data recorded electronically. SAE data will be recorded directly into the trial database (source data will be medical records).

Sites will be required to answer data queries raised by ExeCTU in a timely manner within the trial database. A data cleaning work instruction will be provided to sites.

Every effort will be made to collect all PROMS data at each visit. However, a minimum set of questionnaires will be required to be completed by participants at the appropriate visits including the ATLFB, BDI and SF-36. If participants decline to answer these questionnaires at the appropriate time points they would not be able to continue in the trial and would be withdrawn from the intervention, see section 8.12. This is due to our key outcome measures being linked to this PROMS data.

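### The protocol is inconsistent on whether stopping trial treatment also ends follow-up, so sites following some of its rules would lose outcomes that the treatment-policy estimand needs

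*Protocol*

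**What the plan says.** **What the analysis needs.** Under Protocol 11.3.3, stopping treatment is handled by treatment policy: "the treatment effect is sought irrespective of the occurrence of an intercurrent event". Section 11.3.1 adds: "The primary statistical analysis will include observed data only". Section 4.3.1 asks for at least 180 days of TLFB data, completed at visit 10.

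**Wording that ends participation in the trial.**
- 8.12, investigator-led list: "the CI and/or PI may discontinue a participant from the trial at any time it is considered necessary for any reason including". The grounds include ineligibility (also retrospective), significant non-compliance, adverse events, disease progression and pregnancy.
- 8.12, overdose: "In the case of an overdose with ketamine, the participant will be withdrawn from the trial".
- 9.8: a participant with an allergic reaction to the study drug should leave the trial. No follow-up clause is attached.
- 9.12: "Persistent non-compliance (attendance <80% for treatment visits i.e. visits 2-8) may lead the participant to be withdrawn from the trial". Again no follow-up clause is attached.
- 12.1, on the core set of TLFB, BDI and SF-36: "If participants decline to answer these questionnaires at the appropriate time points they would not be able to continue in the trial".
- 8.10: "Randomised participants who have completed the treatment phase of the trial (visits 2-8) will be required to attend a 3-month follow-up visit". The 6-month visit is in the same sentence.

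**Wording that ends treatment only, or promises continued assessment.**
- 10.7, overdose: "the participant will be withdrawn from treatment and will be invited to attend follow up visits 9 and 10".
- 9.12, two consecutive missed infusions: treatment stops, and visits 9 and 10 are still offered.
- 8.9.1, intoxicated attendance followed by a missed re-arranged visit: treatment stops and follow-up visits continue.
- 9.7 (intolerable side effects) and 10.6 (pregnancy): removal from treatment.
- 8.12, positive urine ketamine screen: treatment stops and follow-up is offered.
- 8.12, general text: people who stop treatment are still invited to visits 9 and 10 unless they withdraw fully; assessments are to continue where possible; and every effort is to be made to keep collecting them from people who are lost to follow-up or deviate repeatedly.

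**The concern.** A treatment-policy estimand can be estimated without extra assumptions only if outcomes are collected after treatment stops. If a rule removes someone from the trial, the visit 10 TLFB is not collected and the observed-data analysis drops that person's primary outcome.

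The grounds for removal are unlikely to be unrelated to outcome. The arms differ 16-fold in dose (0.8 versus 0.05 mg/kg, section 8.7), so drug reactions may differ by arm. Missed visits may follow a return to drinking, which is the outcome itself. The missing-data analysis in 11.3.4 is multiple imputation under missing at random, an assumption that is hard to defend for removals of this kind.

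Roughly ten sites (section 6) would be reading the same text. A site that removes a participant from the trial and one that keeps the participant in follow-up could both claim to be following the protocol.

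**Working it through.** **1. The rules side by side**

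| Event | Reads as leaving the trial | Reads as leaving treatment only |
|---|---|---|
| Two consecutive missed infusions | 8.12 list (example of non-compliance) | 9.12, with visits 9 and 10 offered |
| Attendance below 80% | 9.12 | nothing specific; 8.12 general text only |
| Adverse event | 8.12 list | 9.7, which points back to 8.12 |
| Allergic reaction | 9.8 | nothing specific |
| Overdose | 8.12, which points to 10.7 | 10.7 |
| Pregnancy | 8.12 list, which points to 10.6 | 10.6 |
| Ineligibility found later | 8.12 list | nothing specific |
| Core questionnaire declined | 12.1, first half of the sentence | 12.1, second half of the same sentence (leaves the intervention), which points to 8.12 |

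Most rows are contradictions. Low attendance, allergy and late ineligibility have no follow-up provision of their own and depend on the general text of 8.12. The 8.12 bullet on missed infusions also cites 9.11, although the rule stands in 9.12.

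**2. The attendance threshold**

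Visits 2 to 8 are seven visits. One missed: 6/7 = 85.7%. Two missed: 5/7 = 71.4%, below 80%. A participant who misses two consecutive infusion visits therefore meets both rules in 9.12: withdrawal from treatment with follow-up offered, and possible withdrawal from the trial.

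**3. Sample size**

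The effect size, SD, power and pre-attrition numbers are redacted in section 11.1, so only the attrition step can be checked, as n/(1 − 0.20):
- Primary outcome: 206/0.8 = 257.5, rounded up to the stated 258. Conversely, 258 × 0.8 = 206.4.
- Percentage of heavy drinking days, which sets the trial size: 224/0.8 = 280, as stated.

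With 280 randomised, evaluable numbers are 280 × 0.80 = 224, 280 × 0.75 = 210 and 280 × 0.70 = 196. At 25% total loss the 210 remaining still exceed the 206 that the primary outcome needs. The shortfall starts when loss exceeds 1 − 206.4/280 = 26.3%.

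**4. Power, if losses did go that far**

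Normal approximation: power = Φ((1.96 + z) × √(n/n₀) − 1.96), where z is the normal quantile of the planned power, assumed to be 80% or 90%.

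| Outcome (n₀) | n | Planned 80% | Planned 90% |
|---|---|---|---|
| Primary (206) | 210 | at least 80% | at least 90% |
| Primary (206) | 196 | 78.0% | 88.5% |
| Percentage of heavy drinking days (224) | 210 | 77.4% | 88.1% |
| Percentage of heavy drinking days (224) | 196 | 74.6% | 85.8% |

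The 25% and 30% losses are assumptions. The protocol does not say how many such withdrawals to expect, or whether they would add to the planned 20%.

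**5. Bias**

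If a share w is removed from one arm only, and those removed average d more heavy drinking days than the rest of that arm, the observed arm mean is too low by w × d. Both inputs are assumed:
- 2% × 20 days = 0.4 days
- 5% × 40 days = 2.0 days
- 10% × 60 days = 6.0 days

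Removal from the low-dose arm would shrink an apparent benefit, and removal from the high-dose arm would enlarge it. Equal w and d in both arms gives 0. People removed for drug reactions need not drink more than the rest, so d could also be near zero or negative.

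**The case against.** The best defence is that the protocol, read as a whole, intends to keep people in follow-up. Overdose and pregnancy in 8.12 point to sections that stop treatment only. Side effects and missed infusions have treatment-only rules in 9.7 and 9.12. Straight after the list, 8.12 commits to continued assessment, and it later extends that to repeated deviators. The 9.12 attendance rule says may, and concerns persistent non-compliance. Section 8.10 requires attendance of completers and 8.12 invites discontinuers, so neither bars follow-up. Data already collected are retained. The two firmest instructions cover uncommon events: 10.7 defines overdose as 50 times the higher dose and does not envisage one, and known ketamine allergy is an exclusion criterion.

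Much of this stands. A reader might infer that every 8.12 ground except the urine ketamine screen means full withdrawal, and that the protocol requires sites to discard these outcomes. The text does not support that. Nor does it support reading 12.1 as an outright removal rule for secondary questionnaires: it also covers the TLFB, and the same sentence speaks of leaving the intervention.

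The defence does not remove the fault. General statements of intent sit beside specific rules that say otherwise, and three grounds have no specific follow-up provision. Partial TLFB data from earlier visits do not meet the 180-day requirement in 4.3.1.

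**Conclusion.** The point holds as an inconsistency: the protocol does not reliably separate the end of treatment from the end of outcome collection. Outcomes are lost only where a site acts on the wording about leaving the trial. The protocol permits this in several places, directs it for allergy, and both directs and contradicts it for overdose.

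The effect on the estimate cannot be sized. A reader might infer a bias of a few days towards the null, but that needs an assumed share removed, an assumed difference in drinking and an assumed arm. The protocol gives none of these, and the sign reverses if removals concentrate in the higher-dose arm. A reader might also infer that any loss beyond 20% erodes power for the primary outcome. It does not: the trial is sized at 280 for the percentage outcome, and the primary outcome falls short only below about 206 evaluable, which is a loss above roughly 26%. Power for the percentage outcome does fall with any loss beyond 20%.

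The case for changing the text rests on the contradictions and on the dependence of the primary analysis on observed data, not on these illustrative figures. It matters while follow-up is running, because outcomes not collected may not be recoverable.

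**What to change.** Reconcile 8.10, 8.12, 9.8, 9.12, 10.6, 10.7 and 12.1 without altering any clinical rule on when treatment stops. What happens clinically after an allergic reaction, overdose or pregnancy is for the trial team to settle.

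- In 8.12, state once that ending trial treatment for any reason does not end outcome collection. All randomised participants are invited to visits 9 and 10 and TLFB collection continues. The exceptions are that the participant withdraws consent for further data collection, or that loss of capacity or detention prevents it under its own consent provision.
- In 9.8, 9.12 and the 8.12 list, refer to that statement and say whether treatment or data collection is meant.
- In 8.10, make the follow-up visits apply to all randomised participants.
- In 12.1, state that declining the BDI or SF-36 does not stop TLFB collection.
- Correct the 8.12 cross-reference from 9.11 to 9.12.

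The cost is one text amendment and a few more attendances at follow-up visits already in the schedule.

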# 8.13 End of trial

The end of the trial will be on completion of data cleaning and database lock. ExeCTU will be responsible for notifying sites, the Sponsor and regulatory authorities as well as submitting the end of trial declaration.

Participants invovlement in the trial will cease after their visit 10. There will however be several voluntary opportunities to take part in including: a) joining an online peer support group of fellow participants (sections 8.7 and 14.10), b) taking part in an interview about their trial experiences within 3 months of their visit 10 (section 8.11), and c) an opportunistic 12m online follow-up for those enrolled in the first year of the trial (section 8.10.1).

#### 9 INVESTIGATIONAL MEDICINAL PRODUCT

#### 9.1 Name and description of investigational medicinal product(s)

The product under test will be ketamine hydrocholoride either 0.8mg/kg or 0.05mg/kg; 50mg/mL or 10mg/ml injection vials/ampoules will be used.

#### 9.2 Regulatory status of the drug

Ketamine is a controlled drug (Class B, Schedule 2).

#### 9.3 **Product Characteristics**

For details of product characteristics refer to the latest summary of product characteristics (SmPC) and the trial pharmacy manual.

#### 9.4 Drug storage and supply

Full details can be found in the trial pharmacy manual. Routine hospital stocks of ketamine will be used for this trial. A drug inventory/dispensing record will be maintained and updated by the authorised unblinded personnel at pharmacy or delegated unblinded site staff on the ward for all drugs provided and dispensed at each trial site. Temperature records will be maintained throughout the trial. Ketamine can be stored at room temperature (0-25°C). Once the ketamine infusion has been made up by pharmacy or the unblinded team, it should be used as soon as possible. At the end of the trial, the drug inventory/dispensing record should not be destroyed without Sponsor authorisation and a file note should be included in the TMF and pharmacy site file (PSF) about where to locate these records. An unblinded person at each trial site is responsible for all drug supplies. Written documentation is mandatory.

The unblinded persons at the sites will keep adequate records of the receipt, preparation, administration and return, quarantine or destruction of the trial medication. They will conceal the accountability forms to blinded personnel and ensure these logs are maintained and kept in the PSF. All data regarding the trial medication must be recorded on the relevant forms provided by ExeCTU or on local pharmacy accountability forms authorised by ExeCTU. Any dispensed but completely unused infusions (where the infusion syringe/bag has not been opened) will be returned to pharmacy and destroyed in line with site pharmacy procedures. Partially unused infusions will be returned to pharmacy and destroyed according to site pharmacy procedures. Therefore, the local controlled drug policy will be followed at the research

REDACTED Version 8.0, 18/JUN/2024; IRAS ID: 1008179 MORE-KARE protocol Page 70 of 105

site to ensure that materials are appropriately destroyed. In all instances a record of this destruction will be kept in accordance with relevant SOPs, to document the return and/or destruction of materials at site.

#### 9.5 Preparation and labelling of Investigational Medicinal Product

Preparation and labelling of the IMP should be completed in accordance with Annex 13 of Good Manufacturing Practice (GMP) guidelines. Labelling exemption will apply and site pharmacies/site unblinded personnel are not required to label hospital stock of ketamine (unless specified within Trust policy, please see the pharmacy manual for further details).

Site pharmacies/site unblinded personnel should attach an infusion label (as defined in the pharmacy manual) to the prepared infusion syringes/bags.

#### 9.6 Dosage schedules

Three infusions will be administered at weekly intervals, one each at visits 2, 4 and 6. Doses will be made up from a neutral glass vial/ampoule with rubber closure and aluminium flip-off cap containing ketamine hydrochloride. The total amount to be delivered will be calculated on the basis of the participant's screening visit weight.

Site pharmacy / unblinded site staff will order ketamine and dispense per participant, added to saline (0.9%) to make up to 50ml solution in syringes/bags for the syringe/infusion pump to infuse intravenously over 40 minutes. Doses will be administered using a computer-controlled syringe pump if a syringe has been prepared, or a computer-controlled infusion pump if an infusion bag has been prepared.

#### 9.7 Dosage modifications

No dose modification will be permitted in this trial. If intolerable side effects are experienced, the participant will be withdrawn from treatment (see section 8.12).

